#### 5.1.6 Dose De-escalation Decision Rules:

If a DLT is reached in the first cycle for a given patient, then the previous dose level will be utilized for that particular patient in subsequent cycles. Should that patient experience a second DLT at that lower dose, they will be removed from the study. Dose-escalation will resume until the maximally administered dose is achieved or MTD is reached.

For example, according to the schema in Table 2, if DLT is reached at dose level 1 (romidepsin 10 mg/m^2 and oral 5-azacitidine 100 mg/m^2), the frequency of romidepsin will be reduced to a Day 8 only dose. Dose escalation can resume starting at that point according to dose escalation rules (Table 3). The same

applies if DLT is reached at all other levels prior to dose level four.

Toxicities in cycles 2 and following may be accommodated by treating patients at one dose level below the present cohort. Toxicity in cycles 2 and beyond will not affect dose escalation for future patients.

In the Phase 2, de-escalation should follow the Phase 1 escalation guidelines. For instance, any recurrent Grade 3 toxicity, up to 3 de-escalations will be allowed, with the doses of the drugs being reduced to that described in Cohort 5 (azacytidine 300 mg Day 1-14, and romidepsin 14 mg/m^2 Day 8 and 15 every 28 days) → Cohort 4 (azacytidine 300 mg Day 1-14, and romidepsin 10 mg/m^2 Day 8 and 15 every 28 days) and then Cohort 3 (azacytidine 200 mg Day 1-14, and romidepsin 10 mg/m^2 Day 8 and 15 every 28 days). Any patient experiencing a Grade 4 toxicity should just be immediately dose reduced according to the guideline above. In addition, patients can be dose reduced per the treating physicians discretion.

Specifically, for hematologic toxicities, patients may receive GCSF for neutropenia. For cases where patients miss a dose secondary to a recurrent Grade 3 ANC or platelet count, or Grade 4 hematologic toxicity, dose reductions should occur as noted above at the physicians discretion (i.e. reduce to Cohort 5, then 4 then 3).

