**TABLE 8: Dose Modifications for Romidepsin**

Dose Modifications for Romidepsin	
CTCAE Grade or Abnormal Value	Romidepsin
Thrombocytopenia	
Grade 1 ( $75 \times 10^9/L - < LLN$ ) Grade 2 ( $50 - < 75 \times 10^9/L$ )	Maintain dose level Maintain dose level
Grade 3 or 4 thrombocytopenia:  OR  Thrombocytopenia that requires platelet transfusion or recurrent Grade 3 or 4 thrombocytopenia	Hold subsequent doses of therapy until thrombocytopenia returns to $\leq$ Grade 2 or baseline and continue at full dose  Hold subsequent doses of therapy until thrombocytopenia returns to $\leq$ Grade 2 or baseline and permanently reduce dose of romidepsin to the next reduced level below.. If the same toxicity recurs despite dose reduction, patients should be taken off study.
Neutropenia (ANC)	
Grade 1 ( $1.5 \times 10^9/L - < LLN$ ) Grade 2 ( $1.0 - < 1.5 \times 10^9/L$ )	Maintain dose level Maintain dose level
Grade 3 and 4 neutropenia:	Hold subsequent doses of therapy until specific cytopenia returns to $\leq$ Grade 1 or baseline and continue at full dose
Febrile Neutropenia	
Febrile ( $\geq 38.5^{\circ}C$ ) Grade 4 neutropenia or recurrent Grade 3 or 4 neutropenia:	Hold subsequent doses of therapy until neutropenia returns to $\leq$ Grade 1 or baseline and permanently reduce dose of romidepsin to the next reduced level below.. If the same toxicity recurs despite dose reduction, patients should be taken off study
All Other Non-Hematologic Drug Toxicities (not mentioned in previous tables)	
Grade 1 or 2:	Maintain dose level
Grade 3	Hold treatment with romidepsin until toxicity returns to $\leq$ Grade 1 or baseline, then restart therapy at full dose. If Grade 3 toxicity recurs, reduce dose of romidepsin to the next reduced level below.. This is a permanent dose reduction.
Grade 4	Grade 4 toxicity: Hold treatment with romidepsin until toxicity returns to $\leq$ Grade 1 or baseline, and then restart therapy at the next reduced level below.. This is a permanent dose reduction

Dose interruption or study discontinuation is not required for lymphopenia of any grade.

In general, if study drug has been held and the toxicity does not resolve, as defined above, then drug must

be discontinued.

Note: Dose reductions should not be performed for alopecia or for nausea or vomiting that was not treated with aggressive anti-emetic support.

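### For a first uncomplicated Grade 4 platelet or neutrophil event in Phase II, Section 5.1.6 and Table 8 give three different dosing instructions, and no clear precedence is set

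*Combined protocol and SAP*

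**What the plan says.** Three places in the current protocol speak to the dose after a Grade 4 cytopenia in Phase II.

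- **Section 5.1.6, Phase 2 paragraph.** After listing up to three de-escalation steps for recurrent Grade 3 toxicity, it adds: "Any patient experiencing a Grade 4 toxicity should just be immediately dose reduced according to the guideline above". It makes no exception for a first event or for blood counts.
- **Section 5.1.6, next paragraph, on hematologic toxicity.** The trigger is "For cases where patients miss a dose secondary to a recurrent Grade 3 ANC or platelet count, or Grade 4 hematologic toxicity". The instruction is that "dose reductions should occur as noted above at the physicians discretion".
- **Section 6.3.1, Table 8 (Dose Modifications for Romidepsin).** For Grade 3 or 4 thrombocytopenia, hold until recovery to no worse than "Grade 2 or baseline and continue at full dose". For Grade 3 and 4 neutropenia, hold until recovery to no worse than "Grade 1 or baseline and continue at full dose". The sentence introducing the table applies it to toxicities seen at any time, other than the cardiac ones handled just before it.

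Table 8 also has rows that reduce romidepsin permanently: thrombocytopenia that needs platelet transfusion or recurs, and neutropenia that is febrile at Grade 4 or recurs at Grade 3 or 4.

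**The concern.** The event is a first Grade 4 thrombocytopenia without transfusion, or a first Grade 4 neutropenia without fever. Depending on where the treating physician looks, the next dose is reduced as a matter of course, reduced at the physician's choice, or given in full after a hold. Two patients with the same event could receive different regimens, and both would be within the protocol.

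At stake are the dose given after a severe toxicity and the interpretability of Phase II delivered dose and safety results, which would partly reflect the section followed. The Section 2.4.2 summary shows that the event types are not hypothetical: the two dose-limiting toxicities at the maximum administered dose were one Grade 4 thrombocytopenia and one Grade 4 neutropenia.

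**Working it through.** The plan states no figure on this point to reproduce. The check is a comparison of texts, followed by arithmetic on planned dose.

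**1. Instructions for the event defined above**

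| Source | Condition | Dose afterwards | Drugs affected |
|---|---|---|---|
| 5.1.6, general Grade 4 sentence | Any Grade 4 toxicity | Reduced at once by the listed steps | Combined regimen and cycle length |
| 5.1.6, hematologic paragraph | A dose missed because of Grade 4 hematologic toxicity | Reduction left to the physician | Combined regimen and cycle length |
| Table 8 | Grade 3 or 4 count, not transfused, not febrile Grade 4, not recurrent | Full dose after recovery | Romidepsin only |

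**2. Does another passage rank them?**

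- Section 5.1.2, the Phase 2 regimen description, refers dose modifications to Section 6.
- The thrombocytopenia bullet in Section 5.1.7 refers to Section 6.3.
- Section 6.3 itself, for dose-limiting toxicity after cycle 1, offers the romidepsin package insert or the (de)escalation tables as alternatives, without saying which applies when. That leads back to the Section 5 scheme.

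The pointers favor Section 6, but Section 6 does not close the question.

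**3. Recovery grade for neutropenia**

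Section 6.2 lets treatment restart at the dose used before, once a treatable toxicity (neutropenia is named) is at Grade 2 or less. Table 8 asks for Grade 1 or less, or baseline. By Table 8's own bands, a count from 1.0 to under 1.5 × 10⁹/L is Grade 2. It allows a restart under Section 6.2 but not under Table 8, unless it is the patient's baseline.

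**4. Planned dose after recovery**

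Inputs: the Phase II regimen (Section 5.1.2) is azacitidine 300 mg on Days 1–14 and romidepsin 14 mg/m² on Days 8, 15 and 22 of a 35-day cycle. The first step in 5.1.6 is azacitidine 300 mg on Days 1–14 and romidepsin 14 mg/m² on Days 8 and 15 of a 28-day cycle. I used the doses written out in 5.1.6 because its cohort labels do not match Table 2, where Level 5 is the Phase II regimen itself.

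Romidepsin per week = number of doses × dose ÷ cycle days × 7:

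- Full dose: 3 × 14 ÷ 35 × 7 = 8.4 mg/m²/week
- First 5.1.6 step: 2 × 14 ÷ 28 × 7 = 7.0 mg/m²/week
- Change: 7.0 ÷ 8.4 − 1 = −16.7%

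Azacitidine averaged over the cycle = days × dose ÷ cycle days:

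- Full dose: 14 × 300 ÷ 35 = 120 mg/day
- First 5.1.6 step: 14 × 300 ÷ 28 = 150 mg/day
- Change: 150 ÷ 120 − 1 = +25%

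The first step lowers the average rate of romidepsin and raises that of azacitidine. Table 8 changes neither for this event.

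**5. Number of patients**

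Section 2.4.2 gives 19.2% of 26 patients (5/26) with Grade 3/4 thrombocytopenia, and the same rate for febrile neutropenia. Neither counts the event in question. Grades 3 and 4 are pooled, dose levels are pooled, transfused cases are not separated, and febrile Grade 4 neutropenia already falls in a Table 8 reduction row. The same section reports no toxicities at the MTD.

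**The case against.** The strongest defense is that specific text governs over general text. The hematologic paragraph of 5.1.6 follows the general Grade 4 sentence and deals with blood counts in particular. On that reading 5.1.6 does not mandate reduction for a cytopenia, and Table 8's hold and return to full dose is one lawful use of the discretion granted. Sections 5.1.2 and 5.1.7 also point to Section 6.

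Part of this stands. It would be too strong to say that 5.1.6 simply requires reduction, or that no cross-reference exists. It does not remove the conflict, for two reasons. The hematologic paragraph applies only when a dose is missed. A Grade 4 count that appears after Day 22 and recovers before the next dose causes no missed dose, so the general sentence still applies. Where the paragraph does apply, a discretionary reduction is still not the fixed instruction in Table 8.

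A reader might also infer three things that the documents do not support.

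- **That Grade 4 lymphopenia is a further contradiction.** Table 8 says: "Dose interruption or study discontinuation is not required for lymphopenia of any grade". It is silent on dose reduction, and a dose can be reduced without interruption.
- **That a patient is re-dosed at a Grade 4 count, or is both reduced and given full dose.** Table 8 requires recovery first, and Section 5.1.3 separately sets neutrophil and platelet minimums before each treatment. The difference lies in the dose after recovery.
- **That the 19.2% rates can be projected onto the 24 Phase II patients.** For the reasons in the last step of the working, they do not measure this event.

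**Conclusion.** The point holds in a narrow form. For a first Grade 4 thrombocytopenia without platelet transfusion, or a first Grade 4 neutropenia without fever, in Phase II, the protocol gives three instructions and sets no clear order among them. For neutropenia, Section 6.2 and Table 8 also disagree on the recovery grade.

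The size is the difference between planned regimens after recovery: −16.7% for weekly romidepsin and +25% for averaged azacitidine at the first 5.1.6 step, compared with full dose. These figures assume that cycles run on schedule and that the steps are the doses written out in 5.1.6.

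The claim does not extend to every Grade 4 cytopenia, because Table 8 also reduces romidepsin for febrile Grade 4 neutropenia and for transfused thrombocytopenia. The number of patients affected cannot be estimated from the documents and could be zero. An effect on the response rate is not shown. The text still needs correcting, because it governs the dose given after a severe toxicity.

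**What to change.** Reconcile Section 5.1.6 (both Phase II statements), Section 6.2, Section 6.3 and Table 8 in Section 6.3.1 for this event. The amended text should:

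- state which section governs dose modification in Phase II;
- say whether the rule applies to romidepsin alone or to both drugs and the cycle length;
- use one recovery criterion for neutropenia throughout;
- remove or align the text that then conflicts.

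The choice of rule, including how much is left to the physician, is a clinical decision for the sponsor and the investigator, and this review takes no position on it. The cost is amendment wording, with no effect on sample size or data collection.

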**Table 2: Dose Escalation Scheme for the Combination of Oral 5-azacitidine and Romidepsin**

Dose Level	Dose Escalation Schedule		Cycle Length
	Oral 5-azacitidine (Flat dose [mg])	Romidepsin (mg/m  rounded to 14mg/m  )	
Level -1	100 (Days 1-14)	10 (Day 8)	28
Level 1	100 (Days 1-14)	10 (D8 & 15)	28
Level 2	200 (Days 1-14)	10 (Day 8 & 15)	28
Level 3	300 (Days 1-14)	10 (Day 8 & 15)	28
Level 4	300 (Days 1-14)	14 (day 8 & 15)	28
Level 5	300 (days 1-14)	14 (Days 8, 15 and 22)	35
Level 6	300 Days (1-21)	14 (Days 8, 15, 22)	35

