### 5.1.2 Regimen Description (Phase 2)

Treatment will be administered on an outpatient basis. Patients will be treated with oral 5-azacytidine and romidepsin at the MTD (i.e the Recommended Phase 2 Dose, or RP2D). The treatment will be administered as follows: oral 5-azacytidine 300 mg (flat dose) Days 1-14 and romidepsin 14 mg/m^2 on Days 8, 15, and 22 on an every 35 day cycle. All patients receiving romidepsin will receive potassium and magnesium supplementation as recommended in the package insert of the product. In all cycles romidepsin will be administered first over 4 hours. Reported adverse events and potential risks for oral 5-azacitidine and romidepsin are described in Section 7. Appropriate dose modifications are described in Section 6. No investigational or commercial agents or therapies other than those described may be administered with the intent to treat the patient's malignancy.

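### Section 5.1.6 labels the Phase II dose-reduction steps with cohort numbers that mean other regimens elsewhere in the protocol, so the label-only haematologic rule can be read as no reduction at the first step

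*Combined protocol and SAP*

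**What the plan says.** The Phase II regimen in section 5.1.2 is "oral 5-azacytidine 300 mg (flat dose) Days 1-14 and romidepsin 14 mg/m 2 on Days 8, 15, and 22 on an every 35 day cycle". Table 2 (printed in the synopsis and in 5.1.1) has the same regimen as Level 5: azacitidine 300 mg for 14 days, romidepsin "14 (Days 8, 15 and 22"), 35-day cycle.

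Section 5.1.6 states "In the Phase 2, de-escalation should follow the Phase 1 escalation guidelines" and then writes out up to three steps:

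- The first step is "Cohort 5 (azacytidine 300 mg Day 1-14, and romidepsin 14 mg/m 2 Day 8 and 15 every 28 days").
- The second step, labelled Cohort 4, differs from the first only in that romidepsin falls to 10 mg/m² per infusion.
- The third step is "Cohort 3 (azacytidine 200 mg Day 1-14, and romidepsin 10 mg/m 2 Day 8 and 15 every 28 days").

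The closing paragraph of 5.1.6 deals with haematologic toxicity. For a dose missed because of recurrent Grade 3 counts or Grade 4 haematologic toxicity, it refers back to the preceding text, leaves the decision to the physician, and summarises the steps by label only: "i.e. reduce to Cohort 5, then 4 then 3".

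Two other places number the cohorts. The synopsis, under Treatment Plan (Phase I), assigns the Day 22 infusion and the 35-day cycle to dose cohorts 5 and 6, and the 21-day azacitidine schedule to dose cohort 6. Section 2.4.2, which reports Phase I as conducted, calls the 200 mg level repeated on a 28-day cycle cohort 3, and calls the 21-day azacitidine schedule cohort 7.

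**The concern.** One label, Cohort 5, stands for two regimens. In 5.1.6 it is a step below the Phase II dose. By the synopsis and Table 2 numbering it is the Phase II dose itself. The haematologic paragraph gives no doses, so a reader who looks the label up in Table 2, or in the synopsis, finds the regimen the patient is already on.

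Other text in the protocol sends the reader to the table. The worked example earlier in 5.1.6 uses Table 2 levels, section 6.3 refers to the escalation and de-escalation tables, and the romidepsin modification table speaks of the next level below.

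At stake is what is given after a recurrent Grade 3 or a Grade 4 haematologic toxicity. Section 2.4.2 reports Grade 3/4 febrile neutropenia and thrombocytopenia in 19.2% of Phase I patients each. It also says that patients at the MTD had no toxicities, so the documents do not settle how often the rule would be used at the Phase II dose.

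**Working it through.** **Step 1: match each written-out step to Table 2 on dose, days and cycle length.** The last column extends the as-run numbering in 2.4.2. Cohort 3 (200 mg, 28 days) and cohort 7 (21-day azacitidine) are stated there. Cohorts 4 to 6 are inferred by assuming that the levels between were taken in Table 2 order.

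| Regimen | Label in 5.1.6 | Table 2 level | As-run cohort |
|---|---|---|---|
| 300 mg × 14 days; 14 mg/m² × 3; 35 days (Phase II dose) | none | 5 | 6 (inferred) |
| 300 mg × 14 days; 14 mg/m² × 2; 28 days | Cohort 5 | 4 | 5 (inferred) |
| 300 mg × 14 days; 10 mg/m² × 2; 28 days | Cohort 4 | 3 | 4 (inferred) |
| 200 mg × 14 days; 10 mg/m² × 2; 28 days | Cohort 3 | 2 | 3 (stated) |

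Every label in 5.1.6 is one above the Table 2 level and equal to the as-run cohort number. The regimens are the three Table 2 levels directly below the Phase II dose, in order.

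**Step 2: read the label-only rule both ways.**

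- By the written-out doses, the first step is Table 2 Level 4.
- By Table 2 or the synopsis, number 5 is Level 5, which is the Phase II regimen, so the first step is a 0% change.

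**Step 3: planned dose per week, for the separate query.** The plan states no weekly figure to reproduce. The formula is dose × administrations per cycle ÷ weeks per cycle, with cycles on schedule and no missed doses.

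| Step | Azacitidine, mg/week | Change from Phase II dose | Romidepsin, mg/m²/week | Change from Phase II dose |
|---|---|---|---|---|
| Phase II dose | 300×14/5 = 840 | – | 14×3/5 = 8.4 | – |
| First | 300×14/4 = 1050 | +25.0% | 14×2/4 = 7.0 | −16.7% |
| Second | 300×14/4 = 1050 | +25.0% | 10×2/4 = 5.0 | −40.5% |
| Third | 200×14/4 = 700 | −16.7% | 10×2/4 = 5.0 | −40.5% |

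Azacitidine per cycle is 4200 mg at the Phase II dose and at the first two steps, and 2800 mg at the third. The weekly rise therefore comes wholly from the shorter cycle. Table 2 has the same pattern: 1050 mg/week at Levels 3 and 4, and 840 mg/week at Level 5.

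**The case against.** The strongest reply is that the intended doses can be recovered. They are written out in full one paragraph before the label-only text, which points back to them. A reader would have to ignore that paragraph and then accept an instruction to reduce to the current dose. The as-run numbering in 2.4.2 also makes the labels coherent. This stands as far as it goes and lowers the chance of error. It does not remove the double meaning: the synopsis attaches cohort numbers to Table 2, and the as-run number of the MTD cohort has to be inferred.

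A reader might infer three stronger things that the documents do not support.

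- **That the ladder contradicts Table 2.** It does not. The written-out regimens are Table 2 levels, in the right order.
- **That the 25% rise in weekly azacitidine shows an error.** It is inherited from the cycle lengths in Table 2. Romidepsin falls at the same step, and the protocol nowhere defines a reduction by the weekly amount of each drug.
- **That every Grade 3 or 4 toxicity is exposed to the ambiguity.** The label-only text covers haematologic toxicity; the general rule gives the doses or refers to them.

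Nor do the documents show any effect on the response-rate test in 13.2. Describing dose reductions is a Phase I secondary objective and is not listed for Phase II.

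**Conclusion.** The point holds as a labelling conflict in a toxicity rule that is in force during Phase II. Cohort 5 denotes the full Phase II regimen by the synopsis and Table 2, and a different regimen in 5.1.6, with no map between the two numberings. For the haematologic rule, the two readings of the first step differ by a 16.7% fall in planned weekly romidepsin against no change.

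The explanation by as-run numbering is an inference from two stated cohorts, though it fits all three labels.

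The weekly azacitidine pattern (840, 1050, 1050, 700 mg) is a separate question of intent and is no part of the conflict. It assumes cycles given on schedule. Section 5.1.6 speaks only of Phase II. The exploratory cohort shares the Phase II treatment plan, but nothing says outright that the ladder applies to it.

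**What to change.** Reconcile the synopsis (Treatment Plan, Phase I), both printings of Table 2, section 2.4.2 and section 5.1.6. Use one numbering throughout, or print a map from as-run cohort to Table 2 level. Wherever the ladder is cited, including the haematologic paragraph, list dose, days and cycle length for each step so that no reader depends on a label.

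Ask the investigators to confirm that the move from a 35-day to a 28-day cycle at the first step is intended, and to state whether the ladder applies to the exploratory cohort. Which regimen belongs at each step is for the sponsor and the investigators to settle.

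The cost is a wording amendment. Sample size, error rates and analysis are unchanged.

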### **5.1.7 Prophylactic Medicines and Supportive Care**

Romidepsin is moderately emetogenic. Standard institutional guidelines for anti-emetics will be used. Supportive treatment may include additional anti-emetics, anti-diarrheal, anti-pyretics, anti-histamines, analgesics, antibiotics, and blood products. Patients who experience indigestion or gastroesophageal reflux symptoms on Romidepsin may be treated with Proton Pump Inhibitors (PPIs) as well as H2 blockers as clinically indicated.

Patients who have pre-existing chronic anemia prior to receiving oral 5-azacitidine and romidepsin may continue to receive erythropoietin or darbepoietin. Post cycle 1, colony stimulating growth factors (e.g., filgrastim, peg-filgrastim, and sargramostim) may be used in patients who experience hematological toxicity per American Society of Clinical Oncology (ASCO) guidelines. After initiating treatment, anemia may be managed with growth factors according to the ASCO guidelines: 2006 Update of Recommendations for the Use of White Blood Cell Growth Factors: An Evidence-Based Clinical Practice Guideline <http://www.jco.org/cgi/content/full/24/19/3187>. Neulasta should only be used if the interval to the next dose is ≥14 days.

Patients will be permitted to receive appropriate supportive care measures as deemed necessary by the treating physician including but not limited to the items outlined below:

- **Diarrhea:** Diarrhea should be treated promptly with appropriate supportive care, including loperamide. Loperamide should not be taken prophylactically. Patients should be instructed to begin taking loperamide at the first sign of: 1) poorly formed or loose stool, 2) occurrence of more bowel movements than usual in one day or 3) unusually high volume of stool. Loperamide should be taken in the following manner: 4 mg at first onset of diarrhea, then 2 mg after each unformed stool. The daily dose of loperamide should not exceed 16 mg/day. Loperamide should be deferred if blood or mucus is present in the stool or if diarrhea is accompanied by fever. In this setting, appropriate diagnostic microbiologic specimens should be obtained to exclude an infectious etiology. Patients should also be advised to drink liberal quantities of clear fluids.

- **Nausea/vomiting:** Romidepsin is moderately emetogenic. Ondansteron 8 mg IV will be given prior to Romidepsin injections. Nausea and vomiting should be treated aggressively, with agents such as prochlorperazine, metoclopramide, 5-HT-3 inhibitors, or benzodiazepines. Patients should be strongly encouraged to maintain liberal oral fluid intake during therapy, especially during the initial 14 days of each treatment cycle.
- **Fatigue:** May be cumulative with increasing cycles of therapy. Can be treated as indicated by the treating physician.
- **Anemia:** Treatment with oral 5-azacitidine and romidepsin can cause dose-related anemia. Transfusions or erythropoietin may be utilized as clinically indicated for the treatment of anemia, but should be clearly noted as concurrent medications.
- **Thrombocytopenia:** Treatment with Oral 5-azacitidine and Romidepsin can cause dose-related thrombocytopenia. Transfusion of platelets may be used if clinically indicated. Dose modification for thrombocytopenia is allowed in a manner consistent with the guidelines for dose modification (Section [6.3]). Prophylactic folic acid and vitamin B12 supplements may be necessary to reduce hematologic toxicity.
- **Neutropenia:** Prophylactic use of colony-stimulating factors including G-CSF, pegylated G-CSF or GM-CSF should not be utilized during the first cycle of therapy. These factors may be utilized if clinically indicated in subsequent cycles.
- **Hypokalemia or hypomagnesemia** should be corrected prior to administration of Romidepsin, and consideration should be given to monitoring potassium and magnesium in symptomatic patients (e.g. patients with nausea, vomiting, diarrhea, fluid imbalance or cardiac symptoms.)
- **Oral Mucositis:** Oral 5-azacitidine may cause mucositis (includes stomatitis or mucosal inflammation of gastrointestinal and genitourinary tracts); which may require dosage modification. Prophylactic folic acid and vitamin B12 supplements are necessary to reduce treatment-related mucositis.
- **Hepatotoxicity:** Liver function test abnormalities have been observed with Oral 5-azacitidine use. Persistent abnormalities may indicate hepatotoxicity and may require dosage modification.

